## 9 Ethical Considerations

This study is to be conducted in accordance with applicable US government regulations and international standards of Good Clinical Practice, and applicable institutional research policies and procedures.

This protocol and any amendments will be submitted to a properly constituted independent Ethics Committee (EC) or Institutional Review Board (IRB), in agreement with local legal prescriptions, for formal approval of the study conduct. The decision of the EC/IRB concerning the conduct of the study will be made in writing to the investigator and a copy of this decision will be provided to the sponsor before commencement of this study.

All subjects for this study will be provided a consent form describing this study and providing sufficient information for subjects to make an informed decision about their participation in this study. This consent form will be submitted with the protocol for review and approval by the EC/IRB for the study. The formal consent of a subject, using the EC/IRB-approved consent form, must be obtained before that subject undergoes any study procedure. The consent form must be signed by the subject or legally acceptable surrogate, and the investigator-designated research professional obtaining the consent.

### 9.1 Risks

All treatments used in this protocol will be used according to the FDA approved intended use. No unexpected risks should occur. Risks that may be experienced from any injection are swelling bruising, redness, itching, infection, or pain.

There is minimal risk to this study. This study is a prospective observational study of an FDA approved cosmetic drugs used as approved. The study protocol only adds 3D imaging required to make the observational measurements. The images will be identifying as they are of the face. All identifying images will be stored on a database or computer behind the firewall and a password.

Potential risks of the neuromodulators are:

- dry mouth
- discomfort or pain at the injection site
- tiredness
- headache
- neck pain
- eye problems: double vision, blurred vision, decreased eyesight, drooping eyelids, swelling of your eyelids, and dry eyes.
- drooping eyebrows
- allergic reactions. Symptoms of an allergic reaction may include: itching, rash, red itchy welts, wheezing, asthma symptoms, or dizziness or feeling faint.
- upper respiratory tract infection

Reproductive risks: If patient is of child-bearing potential, a urine pregnancy test may be administered prior to injection to confirm negative pregnancy status. The effects of this drug/device, there could be serious harm to unborn children or children who are breast-feeding. These effects could also harm the mother.

CONFIDENTIAL

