#### **4.6 Vulnerable Populations:**

Children, pregnant women, fetuses, neonates, or prisoners are not included in this research study.

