#### **5.1 Screening**

The screening visit involves patient evaluation of inclusion and exclusion criteria. This information is readily available on the intake visit and does not deviate from standard of care for a clinic visit, including age and past medical history. Once patients are deemed eligible, the process of informed consent will begin. Informed consent will take place.

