##### **5.2.1 Visit 1 (sometimes referred to as the baseline visit)**

Visit 1 involves screening, consent, baseline imaging to measure dynamic strain, randomization, intervention. The subject will be photographed using 3D imaging with multiple facial animations. All pre-procedure images will be evaluated for absolute strain performing two types of facial animation: 1) relaxed, 2) frowning. Following the baseline images, subjects will complete a FACE-Q questionnaire and then randomized to one of the four neuromodulators onabotulinumtoxinA (Botox, Allergan, Irvine, California), abobotulinumtoxinA (Dysport, Ipsen Biopharmaceuticals Inc. Cambridge, MA), incobotulinumtoxinA (Xeomin, Raleigh, NC) or PrabotulinumtoxinA (Jeuveau, Evolus, Newport Beach, California) according to a preset injection plan per FDA approved administration guidelines. The injector will be blinded to the neuromodulator assigned to the subject via randomization at the time of injection in order to decrease any underlying bias during drug administration. The syringes will be documented and prepared by appropriately trained staff.

CONFIDENTIAL

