**TABLE 1 SCHEDULE OF STUDY PROCEDURES**

	Baseline Visit 1	Intervention	Follow-up Visit 2 Day 3	Follow-up Visit 3 Day 30	Follow-up Visit 4 Day 90	Follow-up Visit 5 Day 180
Visit Window	Day 1	Day 1	Day 3 ±1	Day 30 ± 5	Day 90 ±7	Day 180 ±10
Eligibility	X					
Informed Consent	X					
Demographic	X					
Medical History	X					
Consultation	X					
Vectra Photography		X	X	X	X	X
FACE-Q		X	X	X	X	X
Adverse Events	X	X	X	X	X	X

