## **9.4 Informed Consent Process / HIPAA Authorization**

All subjects for this study will be provided a consent form describing this study providing sufficient information for subjects to make an informed decision about their participation in this study. This consent form will be submitted with the protocol for review and approval by the IRB for the study. The formal consent of a subject, using the IRB-approved consent form, must be obtained before that subject undergoes any study procedure. The subject, or legally acceptable surrogate, must sign the consent form, and the investigator-designated research professional obtaining the consent. Subjects will be consented by the study Principal Investigator, or appropriate designee, in a room we have selected in which to perform consent, which is located outside of the clinic. Potential subjects will review the consent form in detail with the person designated to consent (either PI or CRC) and have the ability to take the consent home for further review.

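### The only pregnancy check before injection is an optional, unscheduled urine test, although the protocol says pregnant women are not included

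*Combined protocol and SAP*

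**What the plan says.** The population rule is in section 4.6: "Children, pregnant women, fetuses, neonates, or prisoners are not included in this research study". Section 9.1 gives a reason for it, saying of the treatment that "there could be serious harm to unborn children or children who are breast-feeding". The same paragraph contains the only reference to a pregnancy test in the protocol text: "If patient is of child-bearing potential, a urine pregnancy test may be administered prior to injection to confirm negative pregnancy status".

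The operational sections are silent on the test. Section 5.1 describes screening as a check of the inclusion and exclusion criteria against intake information that "does not deviate from standard of care for a clinic visit, including age and past medical history". It continues: "Once patients are deemed eligible, the process of informed consent will begin". Section 5.2.1 sets out the treatment day: "Visit 1 involves screening, consent, baseline imaging to measure dynamic strain, randomization, intervention". The FACE-Q is completed after the baseline images and before randomization. The schedule, headed "TABLE 1 SCHEDULE OF STUDY PROCEDURES", has rows for eligibility, informed consent, demographics, medical history, consultation, Vectra photography, FACE-Q and adverse events.

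The exclusion lists in 4.4 and the Study Summary do not name pregnancy. Section 4.3 admits women aged 30 to 65.

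**The concern.** A rule on who may be treated needs a required step that checks it. Here the rule is firm, the stated harm is serious, and the check is left to discretion. The *if* clause in 9.1 already limits the test to women of child-bearing potential, so the word *may* leaves open whether those women are tested at all.

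What is at stake is fetal exposure to a cosmetic treatment that the trial itself assigns and supplies free of charge. The woman at risk is one who does not know that she is pregnant: she has nothing to report at history-taking, so nothing prompts the optional test. Section 7.1.2 counts a congenital anomaly or birth defect as a serious adverse event, so a low probability does not make the gap trivial.

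**Working it through.** No arithmetic applies. The check is to follow a woman of child-bearing potential with an unrecognised pregnancy through each step that the protocol text requires, and to ask whether that step would stop the injection.

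1. **Population rule (4.6).** She should not be in the study. This states the rule but gives no means of finding out.
2. **Inclusion and exclusion criteria (4.3, 4.4, Summary).** She is female and can be within the age range. Pregnancy is not on either exclusion list, and these are the criteria that 5.1 says are checked at screening. She passes.
3. **Screening (5.1).** The information used is what a clinic intake yields, with age and past medical history as the examples. A known pregnancy may surface here. An unrecognised one would not reliably do so.
4. **Medical history and consultation (Table 1, baseline column).** The same holds: either may prompt the optional test if pregnancy is suspected, but neither requires it.
5. **Visit 1 sequence (5.2.1).** Screening, consent, imaging, FACE-Q, randomization and injection. No test is listed.
6. **Schedule (Table 1).** None of the eight procedure rows is a pregnancy test.
7. **Reproductive risk paragraph (9.1).** A urine test is foreseen before injection, but only as something that may be done.

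She can therefore complete every required step and be injected with the protocol followed exactly. Section 8.1 has the project manager verify compliance with the protocol, and omitting an optional test is not a departure that this monitoring would flag.

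Two facts bear on where a mandatory test should sit. Section 9.4 says that formal consent "must be obtained before that subject undergoes any study procedure", so a test done for the study comes after consent. Section 9.1 places the test only before injection, which allows it after randomization; a positive result at that point would leave a woman randomised but untreated. Treatment is a single session on Day 1, so one test before it is enough.

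**The case against.** The strongest case on the other side has four parts.

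- **Absence from Table 1 is weak evidence on its own.** The table has no row for randomization or for the injection either, and both are plainly required. This is right: the table is not exhaustive. The point rests on the permissive wording of 9.1 together with the silence of 5.1 and 5.2.1, and the table only fails to correct them.
- **The word *may* could be a notice rather than a rule.** Parts of 9.1 are written as if to the participant, so the sentence could be telling her that a test might be done. That reading is possible. It still leaves the protocol text without a requirement anywhere, so clarification is needed either way.
- **The requirement may sit elsewhere.** Consent forms, case report forms, attachments and institutional policy could each require a test. None was available to read, so nothing can be said about what the site does in practice. If such a requirement exists, 9.1 and the schedule should still agree with it.
- **Section 4.6 already excludes pregnant women, and 5.4 lets the investigator discontinue a subject.** Both are true. Together they imply what a positive result would mean; only explicit wording is missing.

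A reader might also infer from 5.1 that eligibility is finally settled before consent, so that no later test could count. The text does not support this. It says when the consent process starts, not that eligibility cannot be revisited, and 9.1 itself foresees a later check.

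**Conclusion.** The point holds for the protocol text. The protocol excludes pregnant women and warns of possible serious fetal harm, yet no step that it requires would reliably detect an unrecognised pregnancy before the injection. This should be fixed as a matter of participant safety.

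Its size is zero required pregnancy tests. No number of exposed pregnancies is claimed, because the documents give no pregnancy rate, no share of women of child-bearing potential and no testing rate. The conclusion assumes that *may* is read in its ordinary permissive sense and that no unseen study document imposes the test.

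Three stronger inferences are not supported. The documents do not show that pregnant women are allowed in, since 4.6 says the opposite. They do not show that tests are omitted in practice. Nor do they give any ground for an effect on power, type I error or the endpoint.

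**What to change.** - **Section 9.1:** replace the permissive wording with a requirement that the urine test *will be administered to all women of child-bearing potential at Visit 1, after consent and before randomization and injection; a positive result excludes*. The position before randomization should be firm, so that a positive result does not create a randomised but untreated subject. A short definition of child-bearing potential, which the protocol lacks, would keep the rule from being applied by judgement.
- **Section 5.2.1 and Table 1:** add the test to the Visit 1 sequence and as a row marked at Visit 1.
- **Section 4.4 and the Study Summary:** list pregnancy as an exclusion, for consistency with 4.6.

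The cost is a short amendment, one urine test of a kind already foreseen in 9.1 for each woman of child-bearing potential who consents, and possibly a few screen failures. With about 140 women enrolled and one treatment session each, that is at most about 140 tests among those enrolled, plus one for each woman excluded by a positive result. Sample size, randomization method and analysis do not change.

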## **9.2 Benefits**

Subjects participating in this trial may gain insight into the potential benefit of wrinkle reduction in the glabella area from participating in this study. The risks of this study are the same as those that would apply to any injection procedure, such as swelling and low-levels of pain. Additionally, a breach of confidentiality is a possibility although we have created measures to mitigate this risk. Although the benefits may not be readily apparent on an individual basis, the advancement of knowledge gained will serve the medical society and community

There is financial compensation for participation in this study. Subjects will be compensated \$15 for each follow-up visit and questionnaire completed. The payment will be administered after completion of the fourth and final follow-up visit for a maximum total of \$60. The subjects will receive the neuromodulators for no charge.

## **9.3 Risk Benefit Assessment**

Subjects participating in this trial will unlikely experience an increase in risk as this is an observational study of FDA approved neuromodulators. No change in patient care will happen if the subject is consented. All subjects will be asked to return for four follow-up visits for observation and surveys.

## **9.4 Informed Consent Process / HIPAA Authorization**

All subjects for this study will be provided a consent form describing this study providing sufficient information for subjects to make an informed decision about their participation in this study. This consent form will be submitted with the protocol for review and approval by the IRB for the study. The formal consent of a subject, using the IRB-approved consent form, must be obtained before that subject undergoes any study procedure. The subject, or legally acceptable surrogate, must sign the consent form, and the investigator-designated research professional obtaining the consent. Subjects will be consented by the study Principal Investigator, or appropriate designee, in a room we have selected in which to perform consent, which is located outside of the clinic. Potential subjects will review the consent form in detail with the person designated to consent (either PI or CRC) and have the ability to take the consent home for further review.

## **10 Study Finances**

### **10.1 Funding Source**

Funding Sources pending

### **10.2 Conflict of Interest**

None

### **10.3 Subject Stipends or Payments**

There are no subject payments or stipends.

## **11 Publication Plan**

Following data analysis and summary, data will may be presented to relevant conferences and submitted for publication. Once published, data is destroyed.

CONFIDENTIAL

## 13 Attachments

CONFIDENTIAL
